### **3.3 SELECTION OF TRIAL POPULATION**

This study will randomise approximately 120 patients at approximately 50 trial sites. This means that each site should randomise 2-3 patients.

Trial sites are anticipated to mainly be stroke units or neurology wards.

Enrolment will be competitive and will be terminated when the required number of patients have been included into the trial, regardless of enrolment at individual centres. If enrolment is delayed, additional study centres may be recruited.

A log of all patients enrolled into the trial (i.e. who have signed informed consent) will be maintained in the ISF at the investigational site irrespective of whether they have been treated with investigational drug or not.

If a patient is deemed ineligible for a reason which later resolves and all eligibility criteria can be met (e.g. requirement to take specific restricted medication), patients can be re-screened up to one time provided they can still be randomised within 5 to 15 days after start of initial parenteral therapy. Patients cannot be re-screened if any of the following exclusions were met during the initial screening: # 2, 3, 4, 7, 11, 12 and 13.

#### **3.3.1 Main diagnosis for trial entry**

Patients with CVT who are eligible to receive treatment with oral anticoagulation and who meet all other eligibility criteria can enter the trial. CVT should be diagnosed per local practice, using the following techniques:

- MRI+MR venography (preferred) and/or
- CT+CT venography and/or
- MRI or CT in combination with catheter angiography (DSA)

Please refer to Section [8.3.1](#) (Source Documents) for the documentation requirements pertaining to the in- and exclusion criteria.

#### **3.3.2 Inclusion criteria**

1. Written informed consent in accordance with International Conference on Harmonization Good Clinical Practice (GCP) guidelines and local legislation and/or regulations.

Proprietary confidential information © 2017 Boehringer Ingelheim International GmbH or one or more of its affiliated companies

2. Male or female patients. WOCBP must be ready and able to use highly effective methods of birth control per International Conference on Harmonization M3(R2) [R09-1400] that result in a low failure rate of less than 1% per year when used consistently and correctly. A list of contraception methods meeting these criteria is provided Section [4.2.2.4](#) and in the patient information.
3. Age  $\geq$  18 years and  $< 79$  years at Visit 1.
4. Confirmed diagnosis of CVT, with or without ICH.
5. Patient has achieved clinical stability after having received standard acute CVT treatment as required, including anticoagulation therapy for 5-15 days which has been administered until randomisation; anticoagulation must include full-dose LMWH or UFH and may be followed by oral VKA treatment.
6. Eligible for treatment with an oral anticoagulant for their CVT, based on Investigator judgment. Based on risk assessment and clinical condition, patient should be a candidate for at least 24 weeks of oral anticoagulation.
7. Availability of the imaging that was used to diagnose the CVT for the purpose of external review.

### 3.3.3 Exclusion criteria

1. Inability to swallow medications.
2. CVT associated with central nervous system infection.
3. CVT due to head trauma.
4. Planned for surgical treatment for CVT (e.g. decompressive surgery, ear-nose-throat surgery).
5. Conditions associated with increased risk of bleeding such as:
  - Major surgery in the month prior to Visit 1
  - Planned major surgery or intervention in the next 6 months
  - History of intraocular, spinal, retroperitoneal or atraumatic intra-articular bleeding unless the causative factor has been permanently eliminated or repaired per Investigator judgment (e.g. by surgery)
  - Gastrointestinal haemorrhage within the past six months (prior to Visit 1) unless the cause has been permanently eliminated or repaired per Investigator judgment (e.g. by surgery), or endoscopically documented gastroduodenal ulcer disease in the previous 30 days prior to Visit 1

 WOCBP are defined as:

Any female who has experienced menarche and does not meet the criteria for "women not of childbearing potential" as described below.

Women not of childbearing potential are defined as:

Women who are postmenopausal (12 months with no menses without an alternative medical cause) or who are permanently sterilized (e.g., hysterectomy, bilateral oophorectomy or bilateral salpingectomy).

 Diagnosis of CVT will need to be confirmed by means of any (combination) of the following techniques: MRI+MR venography, CT+CT venography and/or MRI or CT in combination with catheter angiography (DSA).

 Definition of "increased bleeding risk" and "major" is per Investigator judgment.

Proprietary confidential information © 2017 Boehringer Ingelheim International GmbH or one or more of its affiliated companies

- Haemorrhagic disorder or bleeding diathesis, e.g. history of thrombocytopenia or platelet count <100,000/ml at screening, von Willebrand disease, haemophilia A or B or other hereditary bleeding disorder, history of prolonged bleeding after surgery/intervention
- Fibrinolytic agents within 48 hours of starting trial medication
- Uncontrolled hypertension (Systolic Blood Pressure (BP) >180mmHg and/or Diastolic BP >100 mmHg)
- Any history of intracranial aneurysm (unless it was permanently resolved with either clipping or coiling at least one year prior to the study entry)

6. Life-threatening or major bleeding (per ISTH criteria, see Section [5.3.5.2](#)) other than ICH due to the index CVT, during the 6 months prior to randomisation or while on anticoagulants during the acute phase of CVT.
7. History of symptomatic non-traumatic ICH with risk of recurrence according to Investigator judgment (including haemorrhagic stroke within 6 months prior to screening, but other than ICH during the acute phase of CVT).
8. Severe renal impairment defined as CrCl (calculated by Cockcroft-Gault equation) <30mL/min at screening, or if the Investigator expects CrCl is likely to drop below 30mL/min during the course of the study.
9. Patients who require taking any of the drugs listed as restricted in Section [4.2.2.1](#) while on active treatment with study drug.
10. Patients receiving treatment with warfarin, dabigatran etexilate or other antithrombotic regimen (i.e. anticoagulants or anti-platelet medication) for an indication other than CVT and requiring continuation of that treatment for the original diagnosis without change in the regimen.
11. Patients with prosthetic heart valves.
12. Known hypersensitivity to dabigatran etexilate or warfarin or to any of the excipients of either product.
13. Any current or recent malignancy ( $\leq$  6 months prior to Visit 1) unless the malignancy was a basal cell carcinoma that was completely removed.
14. Concomitant disease that increases the risk of an adverse reaction to study interventions or with life expectancy < 6 months (for any reason) as per Investigator's judgment.
15. Pre-menopausal women (last menstruation  $\leq$  1 year prior to Visit 1) who are pregnant, nursing, or who plan to become pregnant while in the trial.
16. Patients who have participated in another trial with an investigational drug or device within the past 14 days preceding Visit 1 or who currently are participating in another trial. Patients who are still experiencing a clinical effect from an investigational drug or device.
17. Patients considered unreliable by the Investigator concerning the requirements for follow-up during the study or at the end of the study.
18. Any condition the Investigator believes would not allow safe participation in the study.
19. Active liver disease, as indicated by at least one of the following:
  - Prior and persistent Alanine aminotransferase (ALT (SGPT)) or Aspartate transaminase (AST (SGOT)) or Alkaline Phosphatase  $>3$  x upper limit of normal (ULN)

 Patients participating in a purely observational study will not be excluded.

and/or

- Known Active hepatitis C (as evidenced by positive hepatitis C virus ribonucleic acid assay by sensitive polymerase chain reaction (PCR) based assay, such as Roche Monitor or Bayer TMA assay)  
and/or
- Known Active hepatitis B (HBs antigen positive or anti HBc IgM positive)  
and/or
- Known Active hepatitis A

20. Previous randomisation in this trial.

Note to the eligibility criteria: Pre-randomisation interventional treatment (i.v. r-tPA or urokinase and/or stenting) is neither required nor excluded provided that the start of trial medication is at least 48 hours after the application of any fibrinolytic agent.

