- 3) End of Treatment (EOT) and follow-up procedures (Visits 5 and 6) are performed for all patients at the time of discontinuation of trial medication. This includes patients who discontinue trial medication prior to Day 169 (the Day number does not apply in that case). See also footnotes 4 and 15.
- 4) Extended follow-up applies only to patients who discontinue trial medication early (see Section [3.3.4](#)).
- 5) Re-consenting may become necessary when new relevant information becomes available and should be conducted according to the sponsor's (Boehringer Ingelheim's) instructions.
- 6) National Institutes of Health Stroke Scale (NIHSS) is a tool used to evaluate impairment after a stroke. See Section [5.6.2](#). This neurological assessment is to be completed for the qualifying CVT.
- 7) Height is measured at screening only.
- 8) Pregnancy tests required for all women of childbearing potential. See Section [3.3.2](#) for definition of women of childbearing potential. A urine test is acceptable, unless local regulations demand a serum test to be performed. If a pregnancy test is not routinely performed in female CVT patients, the test at the Screening visit should be performed after informed consent has been obtained.  
In addition to the tests performed at the visits, women of child bearing potential will be supplied with pregnancy tests and instructed to perform pregnancy testing every 4 weeks when visits are more than 4 weeks apart.
- 9) At screening imaging should not be performed specifically for the trial. The imaging that was done for diagnosis of the cerebral venous or dural sinus thrombosis (CVT) will be used and should be submitted for review by the trial's Adjudication Committee (AC). It is expected that CVT is diagnosed and venous occlusion assessed by any of the following techniques: MRI+MR venography, CT+CT venography or MRI or CT in combination with catheter angiography (DSA).
- 10) At EOT the assessment of recanalisation must be done by MRI+MR venography. A separate MRI protocol will be provided as part of the ISF and should be followed for the EOT imaging. The EOT images should be submitted for review by the Adjudication Committee.
- 11) Throughout the trial, whenever routine imaging is performed due to worsening of the patient's condition, a suspected new intracranial haemorrhage or a new venous thrombotic event (VTE), those images are to be made available to the trial's AC for independent blinded review.  

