## **1. INTRODUCTION**

### **1.1 MEDICAL BACKGROUND**

According to the American Heart Association/American Stroke Association (AHA/ASA) Scientific Statement on Diagnosis and Management of Cerebral Venous Thrombosis, published 2011 [[R15-5005](#)], cerebral venous and dural sinus thrombosis (CVT) is a thrombosis of the dural sinus and/or cerebral veins considered to be an uncommon form of stroke. It is estimated that approximately 5 persons per million experience it annually and that it may account for 0.5% to 1% of all strokes. Even large medical centres only admit 5-10 cases in a given year [[R15-5879](#)]. At the same time, CVT can be life-threatening and can have a sustained negative impact on a patient's health status. Approximately 5 percent of patients die in the acute phase of the disorder [[R15-5857](#), [R15-5861](#)]. In addition, the International Study on Cerebral Vein and Dural Sinus Thrombosis (ISCVT) [[R15-4849](#)] found that acute CVT was associated with a 15 percent overall death or dependency rate at the end of follow-up, which varied from 3 to 78 months.

Although the pathophysiology of CVT is not yet completely understood, there are at least two different mechanisms that may contribute to the clinical features of CVT [[R15-5879](#)]:

- Thrombosis of cerebral veins or dural sinus leading to cerebral parenchymal lesions or dysfunction
- Occlusion of dural sinus resulting in decreased cerebrospinal fluid absorption and elevated intracranial pressure

Risk factors for CVT are diverse (e.g. coagulopathies, pregnancy, oral contraception, puerperium, head injury, etc.). It is noteworthy that 75% of all patients suffering CVT are female. The mean age of patients in ISCVT was 39 years [[R15-4849](#)] and only a few CVT patients (less than 10%) are older than 65 years of age.

CVT have a highly variable clinical presentation [[R15-5858](#)] and many of the symptoms are non-specific, making it difficult to diagnose. The onset of symptoms can be acute, sub-acute, or chronic. Symptoms and signs can be grouped in three major syndromes:

- Isolated intracranial hypertension syndrome (headache with or without vomiting in close to 90% of patients, papilledema, and visual problems) [[R15-5851](#)]
- Focal syndrome (focal deficits, seizures, or both)
- Encephalopathy (multifocal signs, mental status changes, stupor, or coma) [[R15-5878](#)]

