	A2.15	Pre-menopausal women (last menstruation ≤ 1 year prior to Visit 1) who are pregnant, nursing, or who plan to become pregnant while in the trial.	Exclusion criterion 15 met as specified in the protocol	None
	A2.16	Patients who have participated in another trial with an investigational drug or device within the past 14 days preceding Visit 1 or who currently are participating in another trial. Patients who are still experiencing a clinical effect from an investigational drug or device.	Exclusion criterion 16 met as specified in the protocol	None
	A2.17	Patients considered unreliable by the Investigator concerning the requirements for follow-up during the trial or at the end of the trial.	Exclusion criterion 17 met as specified in the protocol	None
	A2.18	Any condition the Investigator believes would not allow safe participation in the trial.	Exclusion criterion 18 met as specified in the protocol	None
	A2.19	Active liver disease	Exclusion criterion 19 met as specified in the protocol	None

 TSAP for BI Trial No: 1160.248
 Page 16 of 30

 Proprietary confidential information © 2018 Boehringer Ingelheim International GmbH or one or more of its affiliated companies

Table 6.2: 1 Important protocol violations (continued)

Category /		Description	Requirements	Excluded
Code				from
	A2.20	Previous randomisation in this trial	us randomisation in this trial Exclusion criterion 20 met as specified	
-			in the protocol	
B	D1	Informed consent		. 11
	BI	Informed consent not available/not done	Inclusion criterion 1 not met as	All
	D1		specified in the protocol.	Neue
	B 2	Informed consent too fate	date	None
C		Trial medication and randomisation		
C	C1	Incorrect trial medication taken	Medication kit assigned not matching	PPS
	01	incorrect that incurcation taken	treatment patient was randomised to	115
			(cross-treatment) and/or not matching	
			IRT assignment	
	C2	Randomisation order not followed, e.g.	Cases will be identified from IRT	PPS
		forced randomization, misstratification	reports and read in via the manual PV	
			spreadsheet	
	C3	Non-Compliance	Compliance <80% or >120% over the	PPS
			course of the study for dabigatran	
			patients, or time in therapeutic target	
			range for warfarin patients <45%. See	
			Section 7.3 for details on compliance	
			Non compliance caused by temporary	
			interruption of the treatment due to a	
			procedure or a drop in CrCl to less than	
			30 mL/min should not be classified as a	
			protocol violation.	

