D		Concomitant medication		
	D1	Prohibited medication use	See CTP section 4.2.2.1	PPS
			Those treatments should not be taken	
			during the active treatment phase of the	
			trial:	
			- Fibrinolytic agents (refer to	
			CIP section 4.2.1.5 for	
			CPUb/ULa antagonista (a g	
			- GPH0/IIIa antagonists (e.g.	
			- Rivaroxahan aniyahan and	
			edoxaban, or other oral	
			anticoagulants (e.g. VKAs)	
			- Treatment with systemic	
			ketoconazole, itraconazole,	
			posaconazole, cyclosporine,	
			tacrolimus and dronedarone,	
			and rifampicin, carbamazepine,	
			phenytoin and St. John's Wort	
			Medications will be identified through	
			medical review and details will be	
			provided in the technical TSAP.	

Table 6.2: 1	Important protocol	l violations	(continued)
--------------	--------------------	--------------	-------------

Cate	egory /	Description	Requirements	Excluded
Cod	le	1	•	from
G		Trial Specific Protocol Violations		
	G1	Patient randomized to dabigatran		PPS
		etexilate not withdrawn from trial		
		treatment if CrCl drops to <30mL/min at		
		two different occasions during the trial or		
		drops to <30mL/min and does not		
		recover to above 30 within 7 days		
	G2	Creatinine clearance not measured / not		PPS
		reviewed prior to start of treatment		
	G3	Woman of child bearing potential and		None
		pregnancy test not confirmed to be		
		negative prior to start of trial treatment		
	G4	Woman become pregnant during the trial		None
	G5	Patient on VKA prior to randomization,		PPS
		randomized to dabigatran etexilate and		
		treated although INR not confirmed to be		
		<2.0		
	G6	Patient on VKA prior to randomization,		PPS
		randomized to warfarin and treated		
		although INR not confirmed to be <3.0		
	G7	Patient randomized to warfarin and		PPS
		treated and UFH / LMWH stopped		
		although INR not confirmed to be ≥ 2.0		

The following IPV are programmed automatically: all from A and B, C3, D1, G1, G3-G7.

The remaining IPV are manual IPVs and need to be identified at a site level on the manual PV log.

The frequency of patients with IPVs will be presented. Those which lead to a patient being excluded from the PPS will be presented separately to those which do not.

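### Exclusion criterion 15 and its SAP copy set the menopausal boundary by date of last menses alone, so read literally they miss a nursing woman with more than a year of amenorrhoea

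*Protocol*

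**What the plan says.** **Criterion 15 (Protocol 3.3.3).** The exclusion applies to pre-menopausal women, glossed in a parenthesis as last menstruation no more than "1 year prior to Visit 1) who are pregnant, nursing, or who plan to become pregnant while in the trial".

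**Childbearing potential (footnote to inclusion criterion 2, repeated in Protocol 4.2.2.4).** A woman of childbearing potential (WOCBP) is "Any female who has experienced menarche and does not meet the criteria for" the group not of childbearing potential. That group is "Women who are postmenopausal (12 months with no menses without an alternative medical cause) or who are permanently sterilized". Twelve months without menses is therefore not enough if something else explains it.

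**SAP 6.2, Table 6.2: 1.** Item A2.15 carries the same one-year limit for women "who are pregnant, nursing, or who plan to become pregnant while in the trial" and removes patients from no analysis set. The SAP says that all category A violations are programmed automatically.

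**Related safeguards.**
- Flow Chart footnote 8: "Pregnancy tests required for all women of childbearing potential". Protocol 5.3.3 says the same.
- SAP item G3 records a WOCBP with "pregnancy test not confirmed to be" negative before treatment starts.
- Inclusion criterion 2 requires every WOCBP to be ready and able to use highly effective contraception; SAP item A1.1 records a breach.
- Protocol 3.3.4.1 withdraws from treatment a patient who becomes pregnant. It does not mention nursing.
- Inclusion criterion 6 and exclusion criterion 18 rest on investigator judgement.

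**The concern.** Two parts of the protocol draw the line between pre- and postmenopausal in different places. Criterion 15 uses a calendar limit only. The childbearing-potential definition uses about the same limit but sets it aside when the absence of menses has another medical cause. Lactation is an obvious such cause, and it concerns exactly the women criterion 15 names.

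Participant protection is at stake, not the analysis. Protocol 1.1 says that 75% of patients with this disease are female, gives a mean age of 39 in a large cohort, and states: "Risk factors for CVT are diverse (e.g. coagulopathies, pregnancy, oral contraception, puerperium, head injury, etc". Recently delivered women are an expected part of the recruiting population. Protocol 6.1 allows no eligibility waivers and Protocol 8.3.1 requires documented evidence on every criterion, so sites and monitors will work from the literal text. Because the SAP copies that text, an automated check that follows it would not record the enrolment as a violation of A2.15.

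**Working it through.** The plan gives no figure to reproduce. The check is a comparison of texts, with one day count.

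**Step 1. The same woman under each rule.** Take a nursing woman with no menses for more than 12 months because of pregnancy followed by lactation.

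| Rule | Test applied | Result |
|---|---|---|
| Childbearing-potential definition | 12 months without menses and no other medical cause | Other cause present, so WOCBP |
| Criterion 15, literal | Last menses within 1 year of Visit 1 | Not met, so not excluded |
| SAP A2.15 | Same as criterion 15 | Not recorded |

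**Step 2. Does anything else catch her?** A pregnancy test does not detect nursing. G3 concerns pregnancy tests only. The withdrawal list does not mention nursing. No other criterion names it. What remains is discretionary: inclusion 6 and exclusion 18.

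**Step 3. When does the gap open?** Assumption, not in the documents: delivery occurs 280 days after last menses, range 259 to 294. Time after delivery at which the one-year limit passes = 365 − interval from last menses to delivery.

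- 365 − 280 = 85 days (85 / 7 = 12.1 weeks)
- 365 − 294 = 71 days (71 / 7 = 10.1 weeks)
- 365 − 259 = 106 days (106 / 7 = 15.1 weeks)

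The gap therefore starts roughly 10 to 15 weeks after delivery, for a woman still nursing whose menses have not returned.

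**Step 4. Pregnancy.** On the same assumption a pregnancy dated from last menses ends by day 294 at the latest, which is 365 − 294 = 71 days inside the limit. A pregnant woman falls outside criterion 15 only if she was already amenorrhoeic before conceiving. She is still WOCBP, so she is tested at screening, and G3 applies if a negative result is not confirmed before treatment.

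**Step 5. Planned pregnancy.** A WOCBP planning to conceive during the trial cannot at the same time be ready to use highly effective contraception, so inclusion criterion 2 covers her in substance.

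**Step 6. Numbers.** 0.75 × 120 = 90 women expected. The documents give no rate for nursing women with prolonged amenorrhoea. Purely for illustration, an assumed 0 to 2% gives 0 to 1.8 women (0.02 × 90 = 1.8).

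**The case against.** The strongest reply is that the reading is too literal. A pregnant or nursing woman is pre-menopausal in the ordinary sense, and the parenthesis can be taken as the usual marker of menopause. Few investigators would randomise a nursing mother on the strength of it, and criterion 18 lets them refuse. This shows that the intent is probably wider than the text. It does not remove the ambiguity, and it leaves a named protection to discretion.

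A reader might infer more than the documents support:

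- **That pregnant women can be enrolled and the SAP would not notice.** Steps 4 and 5 answer this. The residue is that no eligibility criterion says a positive test excludes a woman outside criterion 15.
- **That a hormonal intrauterine system opens the gap.** It is on the accepted contraception list and may suppress menses, but criterion 15 matters only if the woman is also pregnant, nursing or planning pregnancy. Amenorrhoea from the device alone changes nothing.
- **That the risk factors in Protocol 1.1 describe the missed patients.** Mostly they do not. Pregnancy lies inside the limit, and so does the puerperium if it is taken as about 6 weeks (assumption): 40 + 6 = 46 weeks, short of 52.
- **That criterion 15 breaches the childbearing-potential definition.** That definition governs contraception and pregnancy testing and is not an exclusion rule. The two boundaries are inconsistent, but no rule is broken.

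These limits stand, and they confine the point essentially to nursing women.

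**Conclusion.** The point holds as a small wording defect with a safety purpose. As written, criterion 15 and A2.15 can pass a nursing woman whom they were evidently meant to exclude, because they lack the medical-cause clause that the protocol uses elsewhere. The conclusion rests on a literal reading of the parenthesis. The 10-to-15-week figure rests on an assumed gestation length.

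Severity is minor. The expected number is very small and may well be zero. A2.15 removes nobody from any analysis set, so neither the sample size nor any estimate is affected.

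**What to change.** Reconcile criterion 15, the footnote to inclusion criterion 2, Protocol 4.2.2.4 and SAP A2.15 so that one boundary applies. There are two ways:

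1. Drop the last-menstruation qualifier from criterion 15, so that it applies to any woman who is pregnant, nursing or planning pregnancy.
2. Replace the qualifier with the protocol's existing WOCBP definition. Because that definition leaves out permanently sterilised women, the sponsor should check that this option treats a nursing woman in that group as intended.

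Whichever is chosen, change A2.15 to match, so that the programmed check follows the same rule. The cost is one protocol line and one SAP row. At most a few women become ineligible, and no analysis has to change.
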